#### *Heart-ROCQ registry*

Data of patients who did not participate, but have given written consent for using routinely collected data, are collected in the Heart-ROCQ registry. Data from the Heart-ROCQ registry are not used for the primary statistical analyses. Separate analyses are performed between included study patients and patients of the Heart-ROCQ registry to get insights into the generalizability of the results of this study. These separate analyses consist of a multivariate analysis of variance (MANOVA) (continue routinely collected baseline parameters (e.g. age, BMI, anxiety for surgery etc.), non-parametric tests (mann whitney test or kruskall-wallis test) for non-normal distributed or ordinal variables (e.g. type of surgery) and chi-square tests for binary parameters (e.g. gender). The included study patients are representative when there are no differences shown with the study registry.

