#### 3.4 Sample size calculation

The composite weighted score consists of a summary score for worsening in functional status and the number of postoperative surgical complications, readmissions to the hospital and major adverse cardiac events (Table 2). The primary endpoint is partly adapted from the A-HeFT study.

The mean weighted score is estimated on 1.0 with a standard deviation of 0.9. This estimation is based on historical data of the UMCG (postoperative surgical complications and mortality), the Fitness Study - an on-going pilot study in the UMCG among the same population - (functional status), two literature studies: Iribarne et al., 2014 (hospital readmissions) and Serruys et al., 2008 (stroke and percutaneous interventions) and Meetbaar Beter database (re-interventions and myocardial infarction). A decrease of 0.3 means on average a decrease of one complication/event or worsening in functional status in 30% (or 10-20% decrease in major cardiac events or death) of the patients, which is considered to be clinically relevant. A group of 286 patients (143 in the PRE+POST group

and 143 in the POST group) achieve 80% power to detect a difference in the weighted score of 0.3, when alpha is set on 0.05.

The number of eligible patients is estimated to be 170 per year. We expect that 100 patients (60%) per year will be enrolled in the study. Therefore the estimated inclusion period is 3.5 years (n=350). In the total sample size (n = 350) a withdrawal of ±20% is incorporated. Because the mean score is estimated on different sources, different interim analyses are performed (section 7.4). Based on the interim analyses, the sample size can be adapted to ensure power.

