### 7.3 Study procedures

#### Inclusion into the study

##### *Elective patients (waiting period > 5 weeks)*

After informing the patients about the surgery the cardiologist checks the inclusion criteria. All eligible patients are informed about the study. If patients express an interest in study participation a patient information letter and informed consent is provided (attachment E1). The researcher will screen the patient for exclusion criteria and asks the patient to give informed consent during routinely preoperative examination. The maximum time between the appointment with the cardiologist and preoperative examination is 14 days; during this period the patient has time for reflection. There will be sufficient time for questions during the meeting with the researcher. In addition, patients are informed that they can withdraw from the study at any time without consequences. The measurements of T1 are performed if the patient meets the study criteria and informed consent is signed. Random allocation is performed after T1 measurements.

Patients who do not want to participate are asked to give written consent (attachment E1.2) for using data, which are collected during routine care. Patients are asked for this Heart-ROCQ study registry to get insight in the possible bias of the included population and thus the generalizability of the results of the study. Data are not used for the primary statistical analyses.

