#### *Potential mediators*

The summary score of the different dimensions of illness representations (IPQ-R) and self-efficacy (CSA) are calculated and handled as continuous variable.

Mean and standard deviation are calculated for continuous variables. Multivariate analyses (inclusive multilevel analyses) are performed to determine time\*group differences for the continuous variables. Non-parametric tests are used if distributions are non-normal. In addition, descriptive statistics will be presented in median and (IQ) range. In all statistical analyses, a two-sided  $p<0.05$  is considered statistically significant.

Missing data analysis will be performed, meaning that the amount and nature of missing data will be studied and depending on this, adequate strategies to handle missing data will be applied (e.g. multilevel analyses). Patients are treated according to the intention to treat principles.

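### The registry comparison reads a non-significant difference as proof that trial patients are representative, and the rule becomes easier to pass the fewer decliners consent

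*Combined protocol and SAP*

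**What the plan says.** Section 9.3, under Heart-ROCQ registry, describes who is in the registry: "Data of patients who did not participate, but have given written consent for using routinely collected data, are collected in the Heart-ROCQ registry". Trial and registry patients are compared on routine baseline variables. Continuous variables go into a MANOVA, non-normal or ordinal variables into rank tests, and binary variables into chi-square tests. The purpose is "to get insights into the generalizability of the results of this study", and the subsection ends with a decision rule: "The included study patients are representative when there are no differences shown with the study registry".

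The rule does not say what counts as a difference being shown. The general statement at the end of section 9.2 supplies it: "In all statistical analyses, a two-sided $p<0.05$ is considered statistically significant".

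Section 7.3 (Inclusion into the study) gives the same reason for the registry, namely to "get insight in the possible bias of the included population and thus the generalizability of the results of the study". Section 9.3 also limits its role: "Data from the Heart-ROCQ registry are not used for the primary statistical analyses".

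The documents give no expected registry size, consent rate, similarity margin, effect-size threshold, power statement or multiplicity rule for this comparison.

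**The concern.** The rule draws a positive conclusion (the sample is representative) from a negative test result (no difference found). A test can be non-significant because the groups are alike or because there are too few patients to tell, and the rule treats both as similarity. It also rewards poor data. Entry to the registry needs separate written consent, so the fewer decliners agree, the less power the tests have and the more readily the trial is called representative.

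The rule can fail in the other direction too. If several variables are tested at 0.05 without adjustment, one may be significant by chance, and a sample that truly is representative would not be called so.

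What is at stake is the statement on generalisability. Selective participation is plausible here. About 40% of eligible patients are expected not to enrol, and one arm asks for a supervised preoperative programme and an inpatient rehabilitation stay. Readers deciding whether the results apply to their own patients could be misled by an unsupported label.

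**Working it through.** **Inputs from the documents.** Section 3.4 gives the recruitment figure ("The number of eligible patients is estimated to be 170 per year"), 100 enrolled per year, an inclusion period of 3.5 years and n = 350. The level of 0.05, two-sided, comes from the end of section 9.2.

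**The plan's own figure.** There is none for the registry comparison. The trial size used as an input does reproduce: a difference of 0.3 with SD 0.9, 80% power and two-sided 0.05 needs 142.2 per arm by t-test, so 143 per arm and 286 in total. Adding 20% withdrawal gives 286 / 0.8 = 357.5, close to the planned 350.

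**Largest possible registry.** 170 × 3.5 = 595 eligible; 595 − 350 = 245 decliners. This size is reached only if every one consents. Sizes of 50 and 100 below are assumptions that show the range.

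**Chance that a single test misses a real difference.** For a standardised difference d, with 350 trial patients and m registry patients:

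SE = √(1/350 + 1/m); power ≈ Φ(d/SE − 1.96); miss rate = 1 − power.

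Example, m = 100 and d = 0.2: SE = √(0.00286 + 0.01) = 0.113; d/SE = 1.76; power = Φ(−0.20) = 42%; miss rate 58%.

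| Registry m | SE | Miss, d = 0.2 | Miss, d = 0.3 | Miss, d = 0.5 | 95% CI half-width (1.96 × SE) |
|---|---|---|---|---|---|
| 50 | 0.151 | 74% | 49% | 9% | 0.30 |
| 100 | 0.113 | 58% | 25% | 1% | 0.22 |
| 245 | 0.083 | 33% | 5% | about 0% | 0.16 |

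A single test misses d = 0.2 more than half the time only when the registry is below about 133, and d = 0.3 only when it is below about 49.

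**The test actually named for continuous variables.** A MANOVA spreads its power over all variables entered. The noncentrality is λ = d² × 350m/(350 + m), with p and 350 + m − p − 1 degrees of freedom. Assume five independent variables, one of which differs by 0.3. The MANOVA then misses it in 72%, 51% and 20% of cases for m = 50, 100 and 245.

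**False alarms when there is no true difference.** With k independent tests at 0.05, the chance of at least one significant result is 1 − 0.95^k.

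- k = 3 (one MANOVA, type of surgery, gender): 1 − 0.95³ = 14%.
- k = 10 (assumed, because the variable lists in section 9.3 are examples only): 1 − 0.95¹⁰ = 40%.

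**The case against.** The strongest reply is that the comparison is descriptive and secondary. Its aim is insight, generalisability is not among the objectives in section 1.1, and registry data stay out of the primary analysis. All of this stands and sets the severity. No treatment estimate or error rate for the trial's endpoints is affected.

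A reader might also infer that the rule will usually be passed even when patients differ. The documents do not support this:

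- Nothing says the registry will be small; the accrual figures allow up to about 245 patients.
- At that size, a single test detects a difference of 0.3 in 95% of cases. With 100 patients it still does so in 75%.
- The rule requires no difference on any test. With ten independent tests and one variable differing by 0.2, the chance of passing all ten is 0.578 × 0.95⁹ = 36% at a registry of 100 and 0.330 × 0.95⁹ = 21% at 245.

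A last objection concerns the remedy. A fixed similarity margin such as ±0.2 on the standardised difference would be hard to meet. The 95% CI half-width exceeds 0.2 whenever the registry is below about 132. At 245 with no true difference, the interval falls inside ±0.2 only about 34% of the time per variable: the estimate must lie within 0.2 − 0.163 = 0.037 of zero, and 2Φ(0.037/0.083) − 1 ≈ 0.34. This is a fair criticism of that margin, and the fix does not use it.

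None of these replies rescues the sentence itself. No margin or effect size elsewhere in the plan gives the lack of a shown difference any meaning as evidence of similarity.

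**Conclusion.** The concern holds as a minor point. The rule is logically unsound at any registry size, and how often it misleads depends on a consent rate the documents do not give. Small differences (0.2) are missed in a third of cases at the largest possible registry and in about three quarters at 50 patients. Moderate differences (0.3) are missed in 5% to 49% over the same range. Large differences (0.5) are mostly detected. False alarms run from about 14% to 40%, depending on the number of tests.

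These figures rest on four assumptions: all 350 planned patients contribute baseline data; the registry has 50, 100 or 245 patients; the 0.05 level from section 9.2 defines a shown difference; and the tests are independent. The consequence stops at the generalisability statement. The documents do not support reading this as a threat to the primary result, or as a rule that nearly always passes.

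**What to change.** Delete the final sentence of the Heart-ROCQ registry subsection in section 9.3 and replace it with wording such as:

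> For each routinely collected baseline variable, the difference between trial and registry patients will be reported with its 95% confidence interval: a standardised difference for continuous and binary variables, and differences in category proportions for type of surgery. The proportion of decliners who consented to the registry will be reported. Generalisability will be judged from the size and precision of these differences, not from p-values.

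If the sponsor wants a similarity margin, it should be set in advance with the achievable registry size in view, using the half-widths in the table above (about 0.16 at 245, 0.22 at 100 and 0.30 at 50).

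The cost is a change of wording; no new data are needed. The downside is that the comparison may have to be called inconclusive if few decliners consent.

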#### **9.4 Interim analysis (if applicable)**

An interim analysis will be performed when 40% of the included patients have conducted the measurements of T6 (one year after surgery). We will be able to determine the actual observed event rate and effect of the two CR programs. The study will be terminated prematurely when one of the CR programs is obviously ( $P<0.001$ ) worse or better than the other CR program. If the event rate is lower than anticipated or when there is little chance of showing that one of the CR programs is better or worse we will decide on possible extending the sample size or discontinuation of the study and write an amendment.

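### Section 9.4 allows the sample to be extended after the between-group effect is seen, with no maximum and an unadjusted final test; if a weak effect triggers the extension, the type I error can rise modestly above 5%

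*Combined protocol and SAP*

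**What the plan says.** Section 9.4 describes one interim: "An interim analysis will be performed when 40% of the included patients have conducted the measurements of T6". Of what it will show, the section says: "We will be able to determine the actual observed event rate and effect of the two CR programs". The study stops if either program is better or worse at P<0.001. Short of that, two conditions open a further decision. The first is "If the event rate is lower than anticipated"; the second is "when there is little chance of showing that one of the CR programs is better or worse". In either case, "we will decide on possible extending the sample size or discontinuation of the study and write an amendment".

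Section 3.4 gives the motive: "Because the mean score is estimated on different sources, different interim analyses are performed". It adds: "Based on the interim analyses, the sample size can be adapted to ensure power". (It speaks of several interim analyses and refers to Section 7.4, which deals with withdrawal; Section 9.4 describes only one.)

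Section 9.1 compares the groups at three months and one year. Section 9.2 sets two-sided p<0.05 for all analyses. None of these sections gives a numerical trigger, a maximum size, a statement that the event rate is viewed pooled over arms, or a final test that allows for a changed sample size. Section 7.2 leaves researchers unblinded and Section 8.5 provides no monitoring board. Section 11.3 has amendments notified to the ethics committee, except non-substantial ones.

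**The concern.** The second trigger is most naturally judged from the observed between-group effect, which Section 9.4 says will be available. Enlarging the trial when that effect is weak, then pooling all patients in an ordinary test, gives the disappointing first stage less weight than planned. Chance findings get a second opportunity, and the ordinary 1.96 cut-off becomes slightly too liberal. A final p just below 0.05 would then not carry a known 5% error rate.

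The stated motive, uncertainty about the mean score, does not require the treatment effect. The plan therefore takes on this risk without needing to.

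**Working it through.** **Inputs from the documents.** Difference 0.3, SD 0.9, alpha 0.05, power 80%, 143 per arm (286), 350 enrolled (Section 3.4); interim at 40% with T6 data and stop at P<0.001 (Section 9.4); final two-sided 0.05 (Section 9.2).

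**The plan's own figure.** The exact two-sample t-test gives 80.2% power at 143 per arm and 79.9% at 142, so 143 per arm reproduces.

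**Assumptions not in the documents.** The trigger is current-trend conditional power (CP) below 20% or 50%, and the final size is 1.5 or 2 times planned (R = 1.5 or 2).

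**Information fraction t, three readings of the 40%.**
- 140/350 = 0.40.
- 140/286 = 0.49, measured against evaluable patients.
- 40% of those enrolled so far. With even accrual ("We expect that 100 patients (60%) per year will be enrolled in the study") and an assumed 0.1 year from enrolment to surgery, (τ − 1.1)/τ = 0.4 gives τ = 1.83 years. Then 73 patients have T6 data and t = 73/350 = 0.21.

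**Method.** Let z1 be the interim statistic.
- CP = Φ((|z1|/√t − 1.96)/√(1−t)). At t = 0.4, CP<20% means |z1|<0.83 and CP<50% means |z1|<1.24. Under the null these occur in 59% and 78% of trials.
- Pooled final statistic: Z = (√t·z1 + √(R−t)·z2)/√R.
- Type I error: reject if |z1|>3.29, otherwise if |Z|>1.96, integrated over the null distribution of z1.

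The mechanism shows at z1 = 0, t = 0.4. The conditional chance of a false positive is 2[1−Φ(1.96·√R/√(R−0.4))], which is 1.1% at R = 1, 2.2% at R = 1.5 and 2.8% at R = 2.

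**Results, one-year comparison** (pairs are CP<20%, CP<50%).

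| t | No extension | Extend to 1.5× | Extend to 2× | Always discontinue |
|---|---|---|---|---|
| 0.21 | 5.06% | 5.34%, 5.42% | 5.48%, 5.60% | 3.82%, 3.01% |
| 0.40 | 5.04% | 5.61%, 5.68% | 5.93%, 6.01% | 4.00%, 3.11% |
| 0.49 | 5.02% | 5.73%, 5.79% | 6.12%, 6.17% | 4.12%, 3.20% |

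A 4-million-trial simulation of one cell (t = 0.4, CP<50%, 2×) gave 6.02%. For scale, 1.5 × 350 = 525 patients, or 5.25 years at 100 per year. With no maximum stated, 5 times planned gives 6.5-6.6%. The least favourable choice of final size at t = 0.4 gives 7.0% even with a cap of 20 times planned.

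**Three-month comparison**, extension triggered by the one-year effect, t = 0.4, assumed correlation 0.5-0.9: 5.2-5.6% at 1.5× and 5.3-5.8% at 2×.

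**Cases with little or no inflation.**
- Re-sizing on the pooled SD (up to 2×), or extending to 1.5× when the pooled mean is below 1.0: 5.0-5.1% (400,000 simulated trials per case, simulation error 0.03 points).
- Mixed conduct at 1.5×: discontinuing 17-45% of low-CP trials brings the error back to 5%.
- Planned-effect CP (difference 0.3, 1.5×, t = 0.4): in the observed direction, 5.0% for CP<20%, only because that rule never fires, and 5.4% for CP<50%. For PRE+POST better by 0.3, 4.8% and 5.2%.

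**Adjusted test.** An inverse-normal combination with fixed weights √0.4 and √0.6 gives 5.04% at all three actual fractions for the one-year comparison, and 5.03-5.04% for the three-month comparison in the cases above.

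**The case against.** The strongest reply is that a rise has not been shown for this trial. The sentence that allows extension also allows discontinuation, which lowers the error. An extension prompted by a pooled event rate adds essentially nothing. The current-trend rule is an assumption, and CP<50% is a generous reading of a small chance, since it fires in 78% of null trials at t = 0.4. All of this stands. Over plausible conduct the error runs from about 3% to 6.2%. A reader might infer that any extension under Section 9.4 inflates the error, or that the plan as written already exceeds 5%. The documents support neither, because the rise belongs only to extension triggered by a weak observed effect and followed by unadjusted pooling.

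A second reply is that an extension needs an amendment, which under Section 11.3 would be notified to the ethics committee. That is a real check, and the amendment could adopt a valid test. However, it would be written after the effect is known, and nothing requires an adjusted test.

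It is also tempting to think that fixing a threshold and a maximum in advance is enough. It is not: every inflated figure above was computed under a fixed rule.

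**Conclusion.** The point holds in a limited form. Section 9.4 permits extension after the effect is seen, with no quantified trigger and no maximum, and Section 9.2 leaves the final test unadjusted. If a weak effect triggers the extension and the data are pooled, the type I error can reach about 5.6-6.0% at t = 0.4 with 1.5-2 times the planned size, or 5.3-6.2% over the three readings of the timing. This rests on the assumed conditional-power trigger and on a normal approximation for a single comparison. It does not address the separate question of testing at two time points. The effect is modest and conditional on how the interim is used. It is worth correcting because the remedy is mainly wording and has to be in place before the interim.

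**What to change.** **Main option.** Before the interim, state that any change in sample size will use only data pooled over both arms: the pooled SD of the one-year composite, with the pooled mean score or event rate. State the calculation, a maximum size and the target difference. Reserve the observed effect for the P<0.001 stop or for discontinuation.

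The target difference needs an explicit choice. With 0.3 held fixed, fewer events tend to lower the SD and shrink the requirement: at SD 0.82, 119 per arm against 143, so no extension would follow. If the target scales with the mean (for illustration, 30% of 0.8 = 0.24), 185 per arm are needed and 143 give 69% power. Without this choice, the low-event-rate trigger in Section 9.4 cannot be carried out.

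The cost is wording, plus giving up extension based on the observed effect. The pooled SD contains the arm difference, but a true 0.3 raises it only to √(0.81 + 0.15²) = 0.912, or 147 per arm instead of 143.

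**If effect-based extension is kept.** Fix the threshold and maximum, and also require an inverse-normal combination test for each primary time point, with weights set in advance (√0.4 and √0.6 if the planned fraction is 40% of the planned size). Define stage 1 by enrolment order or by one year elapsed since surgery, with deaths included and scored as in Table 2. Do not define it by having a T6 visit, which would leave out patients who died although death scores 3 points. Three-month data from later patients must not inform the decision. The primary analysis must be restated as one group contrast per time point, estimated within each stage and then combined.

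The cost at t = 0.4 is about 1 point of power at a true 0.3 (85.9% to 85.0% and 88.7% to 87.7% at 1.5×; 88.1% to 87.4% and 91.8% to 91.0% at 2×, for CP<20% and CP<50%) and 2-3 points at 0.225.

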## 10. ETHICAL CONSIDERATIONS

### 10.1 Regulation statement

This study will be conducted according to the principles of the Declaration of Helsinki (version 8, October 2013) and in accordance with GCP guidelines and Medical Research Involving Human Subjects Act (WMO) and other guidelines, regulations and Acts.

### 10.2 Recruitment and consent

Information is given by the supervising cardiologist when patient is accepted for the surgery. The patient information letter and informed consent will be provided to patients who are interested in the study. Usually a preoperative examination is planned within 5 to 14 days. This time (maximum reflection time of 14 days) can be used for patients to consider their decision. At the preoperative examination, the investigator or research assistant asks the patients if they have read and understood the patient information letter and informed consent. The researcher will give answers when the patient has questions regarding the study. Patients who express that they would like to participate are asked to sign the informed consent, which is also signed by the researcher. The researcher emphasizes that participation or lack of participation is not influencing their treatment. Furthermore, he will explain that withdrawal from the study is possible at any moment (without any consequences or without having the obligation to tell the reason of withdrawal). Patients are included if the written consent is signed.

